## List of Abbreviations

AE	Adverse Event/Adverse Experience
ACASI	Audio/Computer Assisted Survey Instrument
BV	Bacterial vaginosis
CC	CrescentCare Health and Wellness Center
CDC	Centers for Disease Control and Prevention
CFR	Code of Federal Regulations
CIB	Clinical Investigator's Brochure
CRF	Case Report Form
DCC	Data Coordinating Center
DOT	Directly observed therapy
DSMB	Data and Safety Monitoring Board
DSMC	Data and Safety Monitoring Committee
FDA	Food and Drug Administration
FMS	Future microbiota study
FWA	Federal-Wide Assurance
GCP	Good Clinical Practice
HIPAA	Health Insurance Portability and Accountability Act
IB	Investigator's Brochure
ICF	Informed Consent Form
ICH	International Conference on Harmonization
IDE	Investigational Device Exemption
IEC	Independent or Institutional Ethics Committee
IND	Investigational New Drug
IRB	Institutional Review Board
ISM	Independent Safety Monitor
JCHD	Jefferson County Department of Health
LSUHSC	Louisiana State University Health Sciences Center
MSDH	Mississippi Department of Health
MTZ	metronidazole
NAAT	Nucleic acid amplification test
NYU	New York University
N	Number (typically refers to participants)
NDA	New Drug Application
NIAID	National Institute of Allergy and Infectious Diseases, NIH
NIH	National Institutes of Health
OHRP	Office for Human Research Protections
OHSR	Office for Human Subjects Research

Version: 11.0

Version date: 1/2/17

### **List of Abbreviations**

PCR	Polymerase Chain Reaction
PHI	Protected Health Information
PI	Principal Investigator
QA	Quality Assurance
QC	Quality Control
SAE	Serious Adverse Event/Serious Adverse Experience
SOP	Standard Operating Procedure
TOC	Test of Cure
TV	Trichomonas vaginalis
UAB	University of Alabama at Birmingham
UMMC	University of Mississippi Medical Center

## Protocol Summary

Full Title	Trichomonas vaginalis repeat infections among HIV-negative women.
Short Title	TV repeat infections among HIV- women
Clinical Trial Phase	III
IND Sponsor (if applicable)	118276
Conducted By	Tulane University School of Public Health and Tropical Medicine
Principal Investigator	[name].
Sample Size	1664
Study Population	HIV negative women who are TV positive and are the age of majority, English speaking, not pregnant or breast feeding, and are patients at participating clinics; 95% of participants are anticipated to be African American.
Accrual Period	30 months
Study Design	This study is a phase III randomized clinical trial examining two different doses of metronidazole (MTZ) for the treatment of Trichomonas vaginalis (TV). HIV negative women who test positive for TV at their routine exam at participating clinics will be referred to the nurse/study coordinator who will screen for eligibility, provide a description of the study, and obtain written, informed consent (N=1664). Subjects will undergo an audio computer assisted self-interview (ACASI), and will self-collect up to 4 vaginal swabs for InPouch culture and nucleic acid amplification test (NAAT) for TV, Gram stain for bacterial vaginosis (BV) and storage for future microbiota studies (FMS). Subjects will then be randomized into one of two arms: (1) metronidazole (MTZ) 2 g single oral dose (CDC recommended treatment regimen) or (2) MTZ 500 mg oral dose BID for 7 days (CDC alternative treatment regimen) Participants will be scheduled for a Test of Cure (TOC) follow up visit 4 weeks after treatment completion with a window of 3-12 weeks post-baseline for the 2 gm MTZ dose and 4-13 weeks post-baseline for the 7 day MTZ dose. If a woman is NAAT TV+/InPouch TV- at TOC, she may be asked to return for an additional follow up at 4 weeks post TOC visit (window of 3-8 weeks post TOC visit). During follow up visits

[figure not shown]
Version: 11.0

Version date: 1/2/17

	subjects will undergo ACASI and self-collect up to 5 vaginal swabs for TV and BV testing and FMS.
Study Duration	Participants will be enrolled in the study for the time it takes to complete their follow up visits (no more than 21 weeks). Accrual for the study will be 30 months in duration. Participants will be asked for permission to store their samples for future research and for investigators to use their data for secondary data analyses.
Study Agent/Intervention Description	Metronidazole 2g single oral dose under direct observation and Metronidazole 500 mg oral dose BID for 7 days with the first dose given under direct observation
Primary Objective	To examine the influence of two factors on repeat infections with TV among HIV negative women: dosing and the presence of bacterial vaginosis (BV):  We will test two hypotheses: H1: Women receiving multi-day MTZ will be less likely to test TV positive at TOC compared to women who receive the single dose MTZ.  H2: This effect (H1) will only be observed among women who have BV (Nugent score $\geq 7$ ).
Secondary Objectives	To determine the proportion of infections at follow up that are attributable to treatment failure or sexual re-exposure.
Exploratory Objectives	Examination of the rate and factors associated with adherence to medication, knowledge/belief/factors associated with partner treatment, sexual exposure and the nature of the sexual act and sexual partner, and condom use will be possible using the ACASI survey data. These factors will be assessed by arm to determine if any confounding occurred and if so, these analyses will be adjusted for these factors. These data will also help inform future translational research.
Endpoints	Repeat infection with Trichomonas vaginalis (TV) at 4 weeks (TOC) as measured by InPouch culture or NAAT.

**Schematic of Study Design Showing Projected Enrollment:**

Figure 1.  
Randomization Scheme

## 2. BACKGROUND INFORMATION AND SCIENTIFIC RATIONALE

### 2.1 Background Information

*Trichomonas vaginalis* (TV), the most common curable sexually transmitted infection (STI) in the world, is associated with vaginitis, cervicitis, urethritis, low birth weight, preterm delivery, pelvic inflammatory disease and may increase the risk of HSV and HIV acquisition and transmission. Repeat infections are common, ranging from 5%-31%, and share similar sequelae to primary infections. Determining the origin of these repeat infections and examining better treatment options is the focus of this study.

Potential causes of early repeat TV infections include: drug resistance, non-adherence to treatment, clinical treatment failure, or re-infection. Single dose therapy has removed adherence as an issue and *in vitro* resistance testing has consistently demonstrated low rates of insusceptibility. The most likely sources of repeat infections, therefore, are clinical treatment failure (dosing or host factors) or re-infection from an untreated partner.

In our study of TV-infected women who were given directly observed single dose metronidazole (MTZ) and provided with medication to deliver to their sex partner(s), repeat infections rates were high (8%) and nearly all (92%) were attributed to clinical treatment failure. Clinical treatment failure could be due to insufficient dosing or biological factors that interfere with antibiotic treatment. The Centers for Disease Control and Prevention (CDC) guidelines for treatment of TV include: MTZ or tinidazole 2 g single dose as the recommended regimens, and MTZ 500 mg BID 7 day dose as the alternative treatment regimen. These recommendations, however, were based on studies conducted nearly 30 years ago and while single dose was found to be equivalent to multiple dose therapies, repeat TV infection rates after single dose treatment were high (i.e. 5-20%). We recently completed a randomized controlled trial (RCT) among HIV-infected women with TV and found multi-dose MTZ to be superior to single dose treatment. We also found that the presence of bacterial vaginosis (BV) was likely a major factor in the early failure of the single dose treatment. Whether these findings can be extrapolated to HIV-negative women will be examined in aims 1 and 2.

Re-infection from an untreated partner is another potential source of repeat infections. Since TV testing for men is difficult and many TV infected men are asymptomatic, partner treatment is paramount to reducing repeat infections. Patient-delivered partner treatment (PDPT), or the provision of antibiotics to infected index persons to deliver to their sex partners, is a possible alternative to the standard of partner referral (PR) or telling the index woman to refer her partner for care. While PDPT has been found to be superior to standard partner referral methods for reducing repeat Chlamydia and gonorrhea infections, RCTs of PDPT for TV have found conflicting results and, to date, the CDC has not made recommendations to offer PDPT for TV infected women. However, these studies were single centered and likely underpowered, thus larger multi-centered trials are needed.

Given the high prevalence of TV, the absence of a national screening program, the deleterious reproductive outcomes associated with TV and the potential for a TV infection to

increase HIV transmission, reducing repeat TV infections is an important targeted public health approach. The overall goal of this project is to determine the influence of index treatment and host factors on repeat TV infections among HIV-negative women in two specific aims:

**Aim 1: Index treatment- Multi-dose (7 day 500 mg BID - alternative regimen) vs. single dose (2 g – recommended regimen) of MTZ for the treatment of TV.**

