(recommended) is as effective as the multi-dose (alternative) for treatment of *Trichomonas vaginalis* (TV) among HIV+ women. Using a Phase IV randomized clinical trial, HIV-positive women with culture confirmed TV were randomized to treatment arm: MTZ 2 g single dose or MTZ 500 mg BID 7 day dose. All women were given 2 g MTZ doses to deliver to their sex partners. Women were re-cultured for TV at a test-of-cure (TOC) visit occurring 6-12 days after treatment completion. TV-negative women at TOC were re-cultured at a 3 month visit. Repeat TV infection rates were compared between arms. Of the 270 HIV+/TV+ women who were enrolled, the mean age was 40 years, ± 9.4 and 92.2% African-American. Treatment arms were similar with respect to age, race, CD4 count, viral load, ART status, site, and loss-to-follow up. Women in the 7 day arm had: lower repeat TV infection rates at TOC [8.5% (11/130) versus 16.8% (21/125) (R.R. 0.50, 95% CI=0.25, 1.00; p<0.05)], compared to the single dose arm. Because of the known potential for false negatives with TOC culture, we also examined the effect at 3 months and found that the superiority of the approach persisted [3 months [11.0% (8/73) versus 24.1% (19/79) (R.R. 0.46, 95% CI=0.21, 0.98; p=0.03)]. We concluded that the 7 day MTZ dose was more effective than the single dose for the treatment of TV among HIV+ women. (Table 2).

**Altered flora, bacterial vaginosis and TV** - One possible factor in the treatment failure of TV is vaginal flora disturbances. Bacterial vaginosis (BV) is the most common vaginal condition in women of childbearing age. The prevalence of BV in the US ranges from 29% in a nationally

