## **8 STUDY SCHEDULE**

### **8.1 Screening**

Per standard clinic protocol at each site, a patient's clinical examination will include testing for TV. Pregnancy testing by the clinic will follow their standard clinical care guidelines. If the patient self-reports that she is HIV negative, is not pregnant as determined by clinical protocol, not treated for BV and TV positive by wet prep, she will be referred by her clinician to the study personnel for potential enrollment. At sites where NAAT screening is performed, women may be referred because of a NAAT TV+ result. Study staff will discuss the study with the patient, review eligibility criteria and obtain informed consent.

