If a participant's clinical TV positive test result is not confirmed TV-positive by InPouch culture or NAAT, she will be withdrawn from the study. These testing procedures and de-enrollment potential will be fully explained in the consent form. Women will receive \$20 compensation after completion of the baseline enrollment visit. Women will receive a study contact card that has all contact information for study personnel so that she may contact staff in case of appointment change, questions, or adverse events. She will be instructed to keep this card during the course of the study period. If she is withdrawn, she will keep her baseline compensation but told she will not need to attend her follow-up visits.

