## 11.7 Sample Size

### Considerations

[figure not shown]
This RCT will allow for evaluation of index dosing of MTZ by BV status. This study examines two hypotheses simultaneously:

H1: Women receiving multi-day MTZ will be less likely to test TV positive at TOC compared to women who receive the single dose MTZ.

H2: This effect (H1) will only be observed among women who have BV (Nugent score  $\geq 7$ ).

From our pilot work, we found the rates of repeat infection at TOC to be 16.2% for single dose and 10.7% for multi dose at a power of 0.80, we will need 1206 subjects. If we account for a 5% Inner Class Correlation (ICC) for correlation of the subjects within the 4 sites using the formula  $1=(M-1)*ICC$ . We will need to inflate by 15%. We will also inflate by 20% to accommodate for our anticipated follow-up for a required sample size of 1664. We will have 1332 evaluable unites at TOC, which will provide adequate power taking into consideration the ICC.

Figure 1.  
Randomization Scheme

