### **11.13 Final Analysis Plan**

Analyses will be conducted in an intent-to-treat manner with variables categorized per protocol. To assure that randomization has been achieved, selected demographic, clinical and behavioral (including medication adherence and sexual re-exposure) factors will be compared by study arms using chi-square, t-test or ANOVA, where applicable. If randomization was found to be successful (as indicated by even distribution of potential confounders) then analyses will be conducted with no need to adjust for confounding. If randomization was not achieved, then associations will be explored for potential confounding and if found these factors will also be included in the model. From the two aims, there are two hypotheses:

H1: Women receiving multi-day MTZ will be less likely to test TV positive at TOC compared to women who receive the single dose MTZ.

H2: This effect (H1) will only be observed among women who have BV (Nugent score  $\geq 7$ ).

Analysis: The research questions will be answered using a multivariable logistic regression analysis to examine the effect of single versus multi-dose (H1) and the differential impact of BV on this effect (H2). This primary logistic model contains two main effects (i.e. treatment and BV)

Version: 11.0

[figure not shown]
Version date: 1/2/17

and 1 first order interaction (BV by index treatment)). The model (1) will be:  $g(Y_i) = \beta_0 + \beta_1 + \beta_2 + \beta_1 \cdot \beta_2$  where:  $g(Y_i) = \log$  odds of repeat infection,  $\beta_0 =$  coefficient for the intercept,  $\beta_1 =$  (Factor 1) single versus multi-dose,  $\beta_2 =$  (Factor 2) BV at time of visit

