All analyses will be conducted in SAS by Tulane staff under the direction of [name]. Because we will use strict protocols and employ tight supervision of the study sites and the study populations are similar (mostly African American and underserved) we do not anticipate site variations but we will examine for any differences and if found, we will include a site variable in the models. We do not anticipate a three-way interaction, and our simulations (see below) support that belief. We will, however, run a fully parameterized model including all main effects, first order interactions, and second order interaction before running the primary analysis model (1) above. We will consider any p-value less than 0.05 to be significant and any p-value less than 0.10 as near-significant. If there is unexpected significant or near-significant interaction, we will stratify on BV status and assess the impact of index treatment (single vs. multi-dose) and any possible interaction separately for BV positive and BV negative women.

Additional analyses– The ACASI will allow for examination of index adherence to medication, index knowledge of partner treatment, sexual exposure and the nature of the sexual act and sexual partner, condom use. These factors will be assessed by arm to determine if any confounding occurred and if so, these analyses will be adjusted for these factors or stratified by these factors.

**Figure 4:** Algorithm for determining origin of repeat infection at TOC

**Outcome measures** – The study is powered for repeat infections. Since we will have information on sexual exposure and genotyping, we can also refine this outcome measure to examine treatment failure (H1 & H2) and reinfection and will use the algorithm depicted in figure 4.

All analyses will be conducted in SAS by the Tulane staff under the direction of [name]. As the data collection instruments are designed to

minimize missing data we do not anticipate an excessive amount. However, imputation techniques will be utilized to compensate for missing data (e.g. multiple imputation and maximum likelihood). Sensitivity analyses will be conducted to ensure that the method chosen to account for missing data does not bias the study’s results. Additionally, the characteristics of those who complete the study will be compared to those who drop out to determine whether drop out is informative. If not, multiple imputation methods will be used for initial analyses. If,

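### The primary model leaves out the baseline InPouch result, and no culture-based supporting analysis is planned, so a weaker effect than in the HIV-positive trial would be hard to interpret

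*Combined protocol and SAP*

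**What the plan says.** Section 2.1 links this trial to the earlier one in HIV-positive women: "Whether these findings can be extrapolated to HIV-negative women will be examined in aims 1 and 2". In that earlier trial (section 2.2), "HIV-positive women with culture confirmed TV were randomized to treatment arm". Its test of cure was a culture 6-12 days after treatment, with 8.5% positive on the 7-day dose and 16.8% on the single dose (RR 0.50, 95% CI 0.25-1.00).

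Entry is wider here. Wet prep is the usual route, but section 8.1 adds: "At sites where NAAT screening is performed, women may be referred because of a NAAT TV+ result". Under section 8.2, a woman whose clinic result "is not confirmed TV-positive by InPouch culture or NAAT, she will be withdrawn from the study"; either test is therefore enough to stay in. The endpoint (4.2.1) is also either test, at a visit about 4 weeks after treatment.

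Both tests are taken at baseline. Participants "will self-collect up to 4 vaginal swabs for InPouch culture and nucleic acid amplification test (NAAT) for TV" (Protocol Summary). Section 11.4 places the swabs before randomization and says that laboratory personnel are not told the arm.

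Section 11.13 describes the analysis: "This primary logistic model contains two main effects (i.e. treatment and BV", plus one BV-by-treatment interaction. Other factors enter only if the arms prove unbalanced, and site only if sites differ. Baseline InPouch status is not named as a covariate, stratum or subgroup.

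**The concern.** Baseline InPouch is the starting value of one of the two tests that define the endpoint. It comes from a swab taken before randomization and read without knowledge of the arm, so it is a legitimate covariate. It also marks the group closest to the women in the earlier trial. Women who are NAAT-positive and InPouch-negative at baseline may have a different chance of a positive test of cure, or a different response to dose, and the plan merges them with culture-positive women.

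At stake are some power for H1 and, more importantly, the reading of the result against the earlier trial. A risk ratio nearer to 1 than 0.50 could mean that HIV-negative women respond differently, or only that infection was defined more broadly. No planned analysis helps to tell these apart. A culture-positive subgroup added after a disappointing result would be discounted as data-driven.

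**Working it through.** **1. The plan's own figure.** Section 11.7 gives "16.2% for single dose and 10.7% for multi dose at a power of 0.80, we will need 1206 subjects". Section 11.13 says "We will consider any p-value less than 0.05 to be significant"; sidedness is not stated. With p1 = 0.162, p2 = 0.107, mean 0.1345 and a two-sided test:

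n per arm = [1.96√(2 × 0.1345 × 0.8655) + 0.8416√(0.162 × 0.838 + 0.107 × 0.893)]² / 0.055² = 602.9, so 603 per arm and 1206 in all. This reproduces (one-sided gives 950). 1206 × 1.15 × 1.20 = 1664 also reproduces. At the stated 1332 evaluable (666 per arm, taken as independent) the same formula gives power 0.838.

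**2. Power forgone.** The documents give neither the NAAT-only share f nor its risk, so both are assumed: f = 10-50%, and single-dose risk in culture-positive women k = 1 to 5 times that in NAAT-only women. Overall rates are held at 16.2% and 10.7%, with a common odds ratio. BV is left out for simplicity.

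Unadjusted: log OR = ln(0.107/0.893) − ln(0.162/0.838) = −0.478; SE = √[1/(666 × 0.162 × 0.838) + 1/(666 × 0.107 × 0.893)] = 0.1636; Wald power = Φ(0.478/0.1636 − 1.96) = 0.832.

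Adjusted: culture-positive single-dose risk = 0.162/[(1 − f) + f/k]; the common log OR is solved to give 10.7% overall; the SE comes from inverse-variance pooling of the two strata.

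| f | k | log OR | SE | power |
|---|---|---|---|---|
| any | 1 | −0.478 | 0.1636 | 0.832 |
| 30% | 2 | −0.484 | 0.1646 | 0.837 |
| 30% | 3 | −0.490 | 0.1655 | 0.841 |
| 50% | 5 | −0.515 | 0.1697 | 0.858 |

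The gain is 0 to 2.6 points. The SE does not fall; the conditional log OR moves away from zero slightly faster than the SE grows. Simulation at n = 1206 (2000 runs per case) agrees, unadjusted vs adjusted: 80.5% vs 80.2% (20%, 2-fold), 78.9% vs 79.7% (30%, 3-fold), 80.9% vs 82.7% (40%, 3-fold).

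An explained-variance approximation gives the same order. With f = 20-50%, NAAT-only risk r = 4-8% and overall risk p = 0.1345, R² = f(1 − f)(pc − r)²/[p(1 − p)], where pc = (p − fr)/(1 − f). This runs from 0.6% (f = 0.2, r = 0.08, pc = 0.148) to 7.7% (f = 0.5, r = 0.04, pc = 0.229). Power at 666/(1 − R²) per arm is 0.840-0.865, against 0.838.

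**3. Blurring.** Suppose culture-positive women have exactly the earlier rates and NAAT-only women have risk r in both arms. Pooled RR = [(1 − f) × 0.085 + f × r] / [(1 − f) × 0.168 + f × r].

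| f | r | 7-day | single | RR | H1 power at 666 per arm |
|---|---|---|---|---|---|
| 20% | 4% | 0.0760 | 0.1424 | 0.53 | 0.974 |
| 20% | 8% | 0.0840 | 0.1504 | 0.56 | 0.965 |
| 40% | 4% | 0.0670 | 0.1168 | 0.57 | 0.883 |
| 40% | 8% | 0.0830 | 0.1328 | 0.63 | 0.835 |
| 50% | 4% | 0.0625 | 0.1040 | 0.60 | 0.783 |
| 50% | 8% | 0.0825 | 0.1240 | 0.67 | 0.702 |

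The result depends on the assumption. If NAAT-only women had 16.2% in both arms and culture-positive women the planning rates, the pooled RR would be 0.69-0.83 for f = 10-50%, and power 0.748-0.292. Nothing in the documents supports that case over the milder one.

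**4. What a culture-positive analysis could show.** At f = 50% there would be 333 such women per arm, with 333 × 0.168 = 55.9 and 333 × 0.085 = 28.3 events. SE of log RR = √(0.832/55.9 + 0.915/28.3) = 0.217, so RR 0.51 with 95% CI 0.33-0.77. That is informative, though not decisive.

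**The case against.** Several points on the other side stand.

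- **Aims.** A reader might infer that the aims require a culture-based replication and that pooling defeats them. They do not. Aims 1 and 2, the objectives in section 3.1 and H1/H2 concern TV-positive HIV-negative women, without restriction to culture. The link to the earlier trial is a background sentence about its findings.
- **Bias and precision.** A reader might also infer bias or a material loss of precision. Pooling leaves the randomized comparison intact, positivity by either test is a legitimate population, and step 2 shows a small power effect with no fall in the standard error.
- **A false conclusion of no carry-over.** All the illustrative ratios of 0.53-0.67 favour the 7-day dose and lie inside the earlier interval of 0.25-1.00. The weakest is about the effect the trial was sized for (10.7/16.2 = 0.66). H1 power stays at 0.835 or more for shares up to 40%. The dilution also follows from assuming no benefit in NAAT-only women.
- **Inputs.** The share and the risk have no source in the documents. NAAT referral is optional and site-dependent.
- **Comparability.** A culture-based table would still differ from the earlier trial in visit timing and partner medication, and it leans on a test that section 2.2 says gives false negatives at test of cure.

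These points limit the size of the concern. They do not supply the missing analysis: an overall effect weaker than 0.50 would still have two explanations that the plan cannot separate.

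**Conclusion.** The point holds in a limited form. A prognostically relevant baseline result, collected before randomization, is left out of the H1/H2 model, and no analysis brings the result closer to the footing of the trial it is meant to extend. The validity of the primary comparison is not in question.

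The power at issue is about 0 to 3 points over the assumed ranges. The interpretive cost is illustrated by a pooled risk ratio of 0.53-0.67 when culture-positive women respond exactly as before. That rests on an assumed 20-50% NAAT-only share with 4-8% risk and no dose effect in that group. The documents do not support the inference that the trial would probably conclude against carry-over: under these assumptions power falls below the design level only towards a 50% share (0.70-0.78). The change is worth making because it is cheap and is credible only if prespecified.

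**What to change.** In section 11.13:

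1. Add the baseline InPouch result (positive or negative) as a prespecified fixed covariate in the H1/H2 model, kept whatever the balance by arm. This recovers the modest power; as a main effect alone it does not resolve the blurring.
2. Prespecify one analysis, labelled supportive, in women InPouch-positive at baseline. Report the risk ratio with 95% CI for the primary culture-or-NAAT endpoint and, separately, for InPouch alone at test of cure. State beside it that test-of-cure timing (6-12 days then, about 4 weeks now), partner medication (given to all women in the earlier trial) and false-negative cultures limit comparison with 0.50 (0.25-1.00).

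The cost is SAP wording and one table, from results already collected. The primary endpoint and sample size do not change. The odds ratio becomes conditional on baseline culture status, and the supporting analysis has fewer events, so its interval will be wider than one from the same rates in all women. A rule is needed for a missing baseline InPouch result, since section 8.5 discards the swabs of women who refuse treatment after randomization.
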